1. PURPOSE OF PROTOCOL

The pathophysiology of Irritable bowel syndrome (IBS) is multifactorial involving complex interplay of altered intestinal permeability, mucosal immune activation, visceral hypersensitivity and gut dysbiosis. Although the exact triggers for these pathological changes in IBS are not clear but diet might play an important role. In-fact, the majority of patients with IBS report dietary factors as triggers for gastrointestinal symptoms. Fermentable, oligosaccharides, disaccharides, monosaccharides, and polyols (FODMAPs) have been shown to induce IBS symptoms. Several studies have reported improvement in gastrointestinal symptoms on a diet low in FODMAPs (LFD) in patients with IBS, specifically in diarrhea predominant IBS (IBS-D). However, the mechanism of action of LFD is not well understood. Recent data from rodent studies have suggested an increase in colonic permeability and visceral hypersensitivity in response to high FODMAP diet which are reversed on a LFD. However, no human study has investigated the effect of LFD on colonic intestinal permeability. Although a few human studies have investigated the effect of LFD on serum cytokines and fecal microbiome, no study to date has systematically looked into the effect of LFD on mucosal immune cell abundance or mucosal microbiome. We hypothesize that LFD alters mucosal microbiome which, in turn, causes improvement in mucosal immune activation as well as intestinal permeability. In this study, we aim to evaluate the following effects of LFD in patients with IBS-D- i) colonic permeability ii) abundance of colonic mucosal T-cells and mast cell abundance iii) colonic mucosal and fecal microbiome.

2. SIGNIFICANCE AND BACKGROUND FOR THE STUDY

Irritable bowel syndrome (IBS) is a gastrointestinal disorder characterized by abdominal pain and altered bowel habits which affects up to 11% of world population.¹ There is overwhelming evidence that pathophysiology of IBS is multifaceted involving intestinal permeability, mucosal inflammation, mast cell activation, and visceral hypersensitivity.^{2,3} The exact triggers for these physiological changes in IBS are not clear but likely factors include diet and microbial dysbiosis.^{2,3}

Dietary factors are known triggers of IBS related symptoms up to 65% of IBS patients report symptoms attributed to food.⁴ In double-blind, randomized, placebo-controlled trials; fructose and fructans have been shown to induce IBS symptoms in a dose-dependent manner.⁵ In fact, a diet low in fermentable, oligosaccharides, disaccharides, monosaccharides, and polyols (FODMAPs) is the most extensively investigated dietary intervention in IBS.⁶⁻⁸ A recent meta-analysis of seven randomized controlled trials comparing a low FODMAP diet (LFD) with various control interventions in 397 participants suggested a 31% greater likelihood in improvement of global IBS symptoms.⁹ In patients with diarrhea-predominant IBS (IBS-D), Eswaran et al showed that those randomized to LFD had greater reductions in daily scores of abdominal pain, bloating, stool frequency, stool consistency, and urgency than the modified National Institute for Health and Care Excellence (NICE) diet.¹⁰ Others have also shown objective improvement in stool consistency of IBS-D patients with LFD using King's stool chart.⁶

Despite the clinical efficacy of LFD in improving symptoms of IBS-D, its mechanism of action is not clear. Recently, Zhou et al have shown FODMAPs induce colonic tight junction dysfunction and visceral hypersensitivity in rat models, both of which are reversible when rats were fed an LFD.¹¹ They further showed that this effect of FODMAPs is mediated by microbial dysbiosis and elevated fecal lipopolysaccharide level.¹¹ However, studies evaluating the effect of LFD on colonic permeability of humans are lacking. Halmos et al have shown that LFD significantly decreases butyrate producing

3. DESCRIPTION OF RESEARCH PROTOCOL

A. Study Design – Overview, Methods, Procedures

Study Design

Forty consenting IBS-D patients and twenty consenting IBS-C patients will undergo a 7-day screening period beginning with the baseline visit. Patients fulfilling the inclusion and exclusion criteria will undergo a i) flexible sigmoidoscopy to obtain colonic mucosal samples from the recto-sigmoid junction for assessment of intestinal permeability, mucosal immune cell abundance, and mucosal microbiome ii) stool collection for microbiome analysis iii) serological markers of intestinal permeability and iv) saccharide excretion assay. They will then go on a 4-week low FODMAP diet followed by a repeat flexible sigmoidoscopy with biopsies, stool collection, serological markers of intestinal permeability and saccharide excretion assay.

Baseline Visit

- Informed consent will be obtained from the subjects
- Medical history including IBS history will be obtained from the subjects
- Blood samples will be obtained
- Subjects will be instructed on the online questionnaires (described below) to be completed for the duration of the study.
- Subjects will be given a stool collection kit for collection prior to their next visit. The stool will be collected from the subjects' home and brought with frozen icepacks to their next visit.
- Subjects will be given the lactulose-mannitol standard solution and be instructed on urine collection for the test. Subjects will drink the solution first thing in the morning on a day of his or her choice prior to the Initiation Visit and collect of all their urine in a jug for the next 24 hours.

Initiation Visit (7 days post-baseline visit +/- 7 day)

- Subjects will undergo a flexible sigmoidoscopy in MCRU. The flexible sigmoidoscopy will only be performed up to the rectum. Subjects are not required to prep for the procedure (e.g. no diet restrictions or laxatives). Sedation will not be given to the subjects.

- Twelve biopsies will be obtained from the recto-sigmoid junction.
- Subjects will be given the low FODMAP diet instructions. Subjects will be instructed to stay on the low FODMAP diet for 4 weeks.
- Subjects will be given the lactulose-mannitol standard solution and be instructed on urine collection for the test. Subjects will drink the solution first thing in the morning on a day of his or her choice in the week prior to the Post-Diet Visit and collect of all their urine in a jug for the next 24 hours.
- Subjects will be given a stool collection kit for collection prior to their next visit. The stool will be collected at the subject's home in the week prior to the Post-Diet Visit and brought with frozen icepacks to the Post-Diet Visit.

Post-Diet Visit (28 days post-Initiation Visit +/- 5 days)

- Subjects will undergo a flexible sigmoidoscopy in the MCRU. The flexible sigmoidoscopy will only be performed up to the rectum. Subjects are not required to prep for the procedure (e.g. no diet restrictions or laxatives). Sedation will not be given to the subjects.
- Twelve biopsies will be obtained from the recto-sigmoid junction.
- Subjects will return the urine collection container.
- Blood samples will be obtained

Low FODMAP diet

Subjects who consent to participate in the study will be given low FODMAP meals delivered to their home by Epicured at no charge to the subject. Epicured is a meal delivery service that provides ready-to-eat low FODMAP meals. Subjects will be required to provide their home address and name to Epicured in order to receive the delivery 2-3x/week. Epicured will provide 3 meals, 2 snacks and 1 non-water beverage to subjects for each day of the 4 week low FODMAP period. Vegetarian, vegan, and omnivore meals will be provided. Subjects will be told to only ingest Epicured provided items (excluding water).

Healthy Control Arm

The stool of healthy subjects will be collected to compare to the IBS subjects' stool (details of analysis below). These subjects will be recruited from UMIHealthResearch.org. Their medical records will be used to ascertain eligibility and to collect demographic information. The study team will consent and give the subject a stool collection kit. The subjects will return the stool to the study team and their participation in the study will end at that time.

IBS-C Arm

Like IBS-D, the physiological effects of a low FODMAP diet are unclear in patients with IBS-C. The relationship between the physiology of IBS-C and IBS-D, if there any, is also unclear. Thus, as a disease comparison group, 20 patients with IBS-C will be enrolled in the study in order to better understand how a low FODMAP diet effects and changes the microbiome and intestinal permeability of IBS-C patients.

In vivo Intestinal Permeability:

Saccharide excretion assay (Lactulose-Mannitol assay): The test is based on timed urine collection after ingestion of an oral load of two saccharide probes, lactulose and mannitol. In brief, subjects will be required to refrain from ingestion of alcohol, aspirin and NSAIDs for at least 7 days prior to the test. They will also be asked not to consume artificial sweeteners, lactulose, mannitol (2 days prior to the testing) and during the 24-hour testing period. A standard oligosaccharide solution of lactulose (1000 mg), mannitol (100 mg) and flavored rink crystals (1.5 gram) in 250 mL of bottled or tap water, followed by 500 cc of bottled or tap water after 30 minutes, will be ingested. Urine collections will be performed in containers with 5 mL of thymol solution for 0-2, 2-8 and 8-24h following the administration of test sugars and returned to the study center. The total urine volume will be measured, and urinary concentrations of lactulose and mannitol will be measured using high pressure liquid chromatography. The fractional excretion of lactulose and mannitol will be calculated

as the ratio of the total urinary excretion of the respective saccharide probe to the total oral dose of the probe. For each subject, the lactulose–mannitol ratio (LacMan ratio) will be calculated as the fractional excretion of lactulose divided by that of mannitol.

mRNA quantitation

We will use real-time PCR to quantitate mRNA expression of TJ proteins [ZO-1, occludin, claudin-1, 3, 8, 15] and glyceraldehyde 3-phosphate dehydrogenase (GAPDH, control) in colonic biopsies from IBS-D patients.

Colonic biopsies will be submerged in RNAlater Solution (Ambion, Austin, TX) and stored at -80°C. RNA extraction will be performed as in the manufacturer's instructions (RNeasy Mini Kit, Qiagen, Valencia, CA). cDNA synthesis will be performed using 0.2 µg of total RNA with the High Capacity Reverse Transcription Kit (Applied Biosystems, Foster City, CA). Taqman gene expression assays for ZO-1, occludin, claudin-1, 3, 8, 15 and GAPDH will be carried out in duplicate for each gene on an ABI Prism 7900HT Real-time PCR System (Applied Biosystems) according to manufacturer's instructions using the comparative $\Delta\Delta CT$ method for relative quantification. The expression of each gene will be normalized to the endogenous control, GAPDH. This will be performed at the [name] Lab at U of M.

Immunofluorescence for tight junction proteins contract lab

Colonic biopsies obtained pre- and post-dietary intervention will be used for this study. Formalin-fixed tissues will be embedded in paraffin and assembled into tissue microarrays before staining. After de-paraffinization, 5 µm sections will be rehydrated, and antigens will be unmasked by boiling in 0.01 M Tris/EDTA (pH 9.0). Slides will be stained with mouse anti-human ZO-1 monoclonal antibodies (catalog# 33-9100, Thermo Fisher Scientific), occludin polyclonal antibody (catalog# 71-1500, Thermo Fisher Scientific), rabbit polyclonal anti-claudin-1 (catalog# 51-9000, Thermo Fisher Scientific), rabbit polyclonal anti-claudin-3 (NBP1-48526, Novus Biologicals, Littleton, CO), rabbit polyclonal anti-claudin-8 (NBP1-59157, Novus Biologicals, Littleton, CO), rabbit polyclonal anti-claudin-15 (NBP2-13842, Novus Biologicals, Littleton, CO) primary antibodies. Primary antibodies will be detected using Alexa Fluor 594 or 488 conjugated secondary antibodies or highly purified secondary Fab'2 fragments (Jackson ImmunoResearch). Nuclei will be labeled with Hoechst 33342 (H3570, Thermo Fisher Scientific). Stained sections will be mounted in Prolong Diamond (Thermofisher Scientific). Tiled images will be collected on a DM4000 microscope equipped with Chroma filter sets (as above), a 20x HC PLAN APO NA 0.7 objective, CoolSNAP HQ2 grayscale CCD (for fluorescence) and Jenoptik ProgRes C10 Plus color CCD (for transmitted light, i.e., hematoxylin and eosin-stained sections) cameras, and a motorized xyz-stage (Ludl) controlled with custom MetaMorph 7 journals. Post-acquisition processing, including stitching of tiled images and quantitative analysis of signal intensity, will be performed using Metamorph 7 (Molecular Devices Sunnyvale, CA). The samples for this testing will be sent out coded without patient identifiers to the [name] Lab at U of M.

Serological tests for intestinal permeability

Following serological markers for intestinal permeability will be assessed: serum lipopolysaccharide (LPS) activity measured with the Limulus Amebocyte Lysate assay (LAL, Hycult Biotechnology, the Netherlands), and serum zonulin levels (Catalog number 30-ZONSHU-E01; ALPCO, Salem, NH). This will be performed at the [name] Lab at U of M.

Intra-epithelial and lamina propria mononuclear cell isolation

Mononuclear cells will be obtained from colonic intra-epithelial and lamina propria fractions. Intra-epithelial (IELs) and lamina propria lymphocytes (LPs) will be isolated following incubation in dissociation buffer (HBSS Ca^{2+} and Mg^{2+} free containing 2% FBS, 5mM EDTA, 10 mM HEPES) and digestion buffer (HBSS with Ca^{2+} and Mg^{2+} , 10% FBS, 0.5 mg/ml DNase I and 0.5 mg/ml collagenase type IV), resuspension in 40% and layering on 80% Percoll Plus. IELs and LPs viability will be checked by Trypan blue exclusion.

Flow cytometry staining

Cell phenotype will be assessed by flow cytometry following cell incubation with fluorochrome-conjugated anti-human antibodies to: CD3, CD4, CD8, CD45RO, CD45RA, CD25, CD39, CD73, CD56 and CD117 (or c-KIT, marker of mast cell). Frequency of cells positive for FOXP3, RORC, T-bet and GATA-3 - transcription factors of Tregs, Th17, Th1 and Th2 lymphocytes will be assessed by intracellular staining following cell fixation and permeabilization with Cytofix/Cytoperm and incubation with fluorochrome-conjugated anti-human FOXP3, RORC, T-bet and GATA-3. Frequency of cytokine-producing cells will be determined after exposure to phorbol 12-myristate 13-acetate (PMA, 10ng/ml) and Ionomycin (500ng/ml) for 60 minutes and to Brefeldin A (20 μ g/ml) for additional 5 hours. Cells will be acquired on a BD LSRII and analyzed using BD FACSDiva software. 3-5 \times 10⁴ events will be acquired for each sample. Positively stained cell populations will be gated based on unstained, single stained and isotype stained controls. This will be performed at the [name] Lab at U of M.

Immunohistochemistry for immune cells

For immunohistochemistry, 5 μ m colon biopsy sections will be stained for human CD3, CD4, CD8, CD56, CD39, FOXP3, RORC, T-bet, GATA-3 and CD117 (or c-KIT). Endogenous peroxidase blocking with 3% H₂O₂ will be carried out. Sections will be incubated overnight at 4°C with primary antibodies to the above antigens and subsequently exposed to avidin/biotin complex with HRP (Vector Laboratories, Burlingame, CA). ImmPACT DAB (Vector Laboratories) was then applied and sections examined by light microscopy. This will be performed at the [name] Lab at U of M.

Mucosal and fecal microbiome

Two colonic mucosal biopsies and stool samples obtained before and after the dietary intervention would be used for this analysis. Once obtained, each biopsy will be washed using Sterile PBS to remove non-adherent luminal/fecal material. The biopsy samples will be weighed, flash frozen in liquid nitrogen and stored at -80C for DNA extraction and microbiological analysis. DNA extraction will be done using a QIAamp DNA Mini Kit (Qiagen, Crawley, UK) per manufacturer's instructions. Bacterial community composition in isolate DNA samples will be characterized by amplification of the V1-V3 variable regions of the 16sRNA gene by polymerase chain reaction for both mucosal and fecal samples. 16S rRNA PCR products will be quantified, pooled and purified for the sequencing reaction. 454 GS FLX Titanium sequencing will be performed on a 454 Life Science Genome Sequencer FLX machine for both mucosal and fecal samples. Sequencing data generated will be processed by the Quantitative Insights into Microbial Ecology Pipeline (QIIME). Sequences will be screened for chimeras using the ChimeraSlayer algorithm, and all potential chimeras will be excluded from downstream analysis. Sequences less than 200 bp or greater than 1000 bp in length, those with average quality scores <20, incorrect primer sequences, or more than 1 ambiguous base will be excluded from downstream analysis. The quality filtered sequences will be assigned to operational taxonomic units (OTUs; sequences that share \geq 97% similarity) using a closed reference approach in QIIME with the UCLUST algorithm and the Greengenes reference database. According to the results of OTUs analysis, a diversity analysis including Simpson, Shannon, Chao 1, ACE and Good's Coverage will be carried out by QIIME. β diversity metrics, including (UniFrac weighed or unweighted) will also be calculated.

Stool samples will also be obtained from 30 healthy controls aged 18-65 years without any known gastrointestinal history and who do not report any abnormal bowel movements or abdominal pain. Stool samples from healthy controls will be utilized for analyzing fecal microbiome using the methodology described above. Their microbiome will be compared with microbiome of IBS-D patients pre and post LFD.

Clinical variables

Data will be collected and stored via Research Electronic Data Capture (REDCap), a HIPAA compliant, free, secure, web-based application. Patients will be automatically emailed a link daily (via REDCap) with a REDCap link to the questionnaires listed below.

Patients will be asked to complete the IBS-SSS and record their most common stool consistency of

the day (measured using Bristol stool form scale) every day during the baseline period and the last week of 4-week LFD. In addition, following questionnaires will be administered at the end of the baseline period as well as the end of the 4-week LFD.

Patient Reported Outcomes Measurement Information System (PROMIS)

The Patient Reported Outcomes Measurement Information System (PROMIS) is a National Institutes of Health (NIH) set of tools used to provide information on patient outcomes in a variety of fields.

Gastrointestinal PROMIS scales: PROMIS scales of Belly pain and diarrhea will be administered to assess the severity of belly pain and diarrhea in our patients. PROMIS Belly pain questionnaire and PROMIS diarrhea questionnaire have five and six questions, respectively, which assess symptom severity on a 5 point Likert scale. Higher T-scores on these questionnaires refer to more severe gastrointestinal symptoms.

PROMIS belly pain asks how often did you have belly pain, severity of belly pain, interference with activities, bothersomeness and discomfort.

PROMIS diarrhea asks how many days did you have loose stools, interference with activities, bothersomeness, and how often you experience urgency.

Irritable Bowel Syndrome Severity Scoring System (IBS-SSS): (IBS-SSS) is a validated scale for assessing overall IBS symptom severity.²² It includes 5 questions of equal weight concerning symptoms over the past 10 days: average severity of abdominal pain, number of days with abdominal pain, average severity of abdominal distension or bloating, satisfaction with bowel habits, and the overall interference in their quality of life from these symptoms. All questions are scored on a 0-100 scale. The scores for all five questions are summed to a total IBS-SSS score between 0-500. Lower scores indicate lower symptom severity.

Diet compliance: Patients will also be asked to record their day's food and drink intake and record whether they were compliant with the FODMAP diet. Prior to the baseline flexible sigmoidoscopy, patients will be asked to record the previous 3 days' food and drink intake

B. Statistical Considerations

Sample Size Justification: Statistical analysis

All continuous variables will be tested for normality using the Shapiro-Wilk test. Normally distributed continuous data will be presented as mean (\pm SD) and will be compared pre-and post-dietary interventions using paired Student's t-test. Continuous data which are not normally distributed will be presented as median (range) and compared using Wilcoxon signed-rank test. Proportions will be expressed as percentages and compared using chi-square test or fisher exact test as appropriate. Since we anticipate that most of our tests will involve continuous data that is normally distributed, we based our power analysis on pre-post comparisons using paired t-tests. Assuming two-tailed tests, with alpha set at 5%, a sample size of 20 will provide 80% power to detect a medium effect size (i.e., Cohen's d=.5) when the pre-post correlation is r=.7.

C. Subject Selection

Inclusion criteria for IBS subjects

Patients with IBS-D or IBS-C diagnosed per Rome IV questionnaire and without any alarm features (rectal bleeding, weight loss, nocturnal symptoms, family history of inflammatory bowel disease or celiac disease) will be considered for the study if they had:

- i) Aged 18-65 years at the time of screening
- ii) Normal serum studies including serum tissue-transglutaminase antibodies, thyroid stimulating hormone levels, C-reactive protein, complete blood count since the onset of symptoms
- iii) Normal stool studies including, ova and parasites since the onset of symptoms
- iv) IBS-SSS score of ≥ 175 at the end of the 7-day screening period

In case of presence of any alarm features and/or elevated inflammatory markers (C-reactive protein or fecal calprotectin), patients will be eligible if they have been excluded for inflammatory bowel disease with upper endoscopy, and colonoscopy in the last one year.

Exclusion criteria for IBS subjects

- i) individuals already on a LFD or other dietary restriction such as gluten free diet within the past 6 months
- ii) individuals with any known food allergy or insulin-dependent diabetes
- iii) known history of celiac disease, inflammatory bowel disease or microscopic colitis
- iv) prior small bowel or colonic surgery or cholecystectomy
- v) pregnant patients
- vi) Antibiotics in the past 3 months
- vii) Those who regularly use mast cell stabilizers or anti-histaminic or non-steroidal anti inflammatory agents (NSAIDs) excluding daily baby aspirin or steroids or bile-acid binder.

Inclusion criteria for healthy volunteers

Aged 18-65 years

Exclusion criteria for healthy volunteers

1. History of gastrointestinal illness
2. Self-reported constipation, diarrhea, or abdominal pain
3. Antibiotics in the past 3 months
4. Gastroenteritis in the past 3 months

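### On the nominal day-7 schedule, abstention begun at Baseline reaches only 1 to 6 of the 7 days required before the baseline sugar test, against 21 to 27 days of lead time for the post-diet test

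*Combined protocol and SAP*

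**What the plan says.** All the timing rules are in section 3.A of the combined protocol and SAP.

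- **Washout rule** (Saccharide excretion assay): "subjects will be required to refrain from ingestion of alcohol, aspirin and NSAIDs for at least 7 days prior to the test".
- **Baseline test** (Baseline Visit, last bullet): the solution is handed out at that visit and drunk first thing in the morning "on a day of his or her choice prior to the Initiation Visit", followed by a 24-hour urine collection. No earliest day is given.
- **Initiation Visit**: "Initiation Visit (7 days post-baseline visit +/- 7 day".
- **Post-diet test** (Initiation Visit, instructions for the second test): the drink is taken "on a day of his or her choice in the week prior to the Post-Diet Visit", and that visit is defined as "Post-Diet Visit (28 days post-Initiation Visit +/- 5 days".
- **Intake while on the diet** (Low FODMAP diet): "Subjects will be told to only ingest Epicured provided items (excluding water".

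Section 6 describes a short eligibility screen before the first office visit and places the explanation of the study and consent at the Baseline Visit. Neither part mentions a washout. Section 3.C excludes regular NSAID users but, on its natural reading, leaves people on daily baby aspirin eligible.

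**The concern.** The washout rule and the nominal visit schedule do not fit together for a subject who begins abstaining when enrolled. The baseline drink must come before a visit set 7 days after Baseline, so 7 abstinent days cannot accumulate in between. The second test has weeks of lead time, and the supplied-items-only rule further limits alcohol in that period, although it does not mention medicines.

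The shortfall is therefore lopsided. Incomplete washout, chiefly of alcohol and possibly of occasional NSAID or aspirin use, could affect the baseline LacMan ratio more than the post-diet one. Colonic permeability is the first listed aim, and section 3.B analyses it by paired pre/post comparison. Both IBS groups go on the diet and healthy controls give stool only, so no off-diet IBS arm would show a change in LacMan caused by washout rather than by diet.

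**Working it through.** The plan states no count of reachable abstinent days, so there is no figure of its own to reproduce. The check is calendar arithmetic on its stated timings.

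**Baseline test.** Let Baseline be day 0 and Initiation day I. A drink on a day before Initiation means d = 1 to I − 1. The latest choice, the morning of day I − 1, lets the 24-hour collection finish on the morning of day I. Abstinent days since Baseline = d. The rule needs d ≥ 7, so permitted mornings number I − 1 and compliant mornings number max(0, I − 7). If full 24-hour days are counted and the Baseline Visit falls later in the day than the morning drink, the rule needs d ≥ 8 and compliant mornings number max(0, I − 8).

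| Initiation day | Permitted mornings | Compliant, d ≥ 7 | Compliant, d ≥ 8 |
|---|---|---|---|
| 7 (nominal) | 6 | 0 | 0 |
| 8 | 7 | 1 | 0 |
| 9 | 8 | 2 | 1 |
| 10 | 9 | 3 | 2 |
| 14 | 13 | 7 | 6 |

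At I = 7, d runs from 1 to 6, so abstention reaches 1 to 6 days and the shortfall is 7 − 6 = 1 day at best and 7 − 1 = 6 days at worst. Initiation before day 7 lies inside the literal window but is not tabulated: eligibility depends on an IBS-SSS score taken when the 7-day screening period ends (section 3.C). It would leave no compliant morning in any case.

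**Post-diet test.** Let the Post-Diet Visit be P days after Initiation, with P = 28 ± 5, that is 23 to 33. The drink falls on days P − 7 to P − 1 after Initiation:

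- P = 23: days 16 to 22
- P = 28 (nominal): days 21 to 27
- P = 33: days 26 to 32

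Like for like, the nominal comparison is 1 to 6 days against 21 to 27. Across the post-diet window the lead time is 16 to 32 days. Across the baseline window the maximum is 14 − 1 = 13 days.

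**Can existing records show a breach?** Under Diet compliance: "Prior to the baseline flexible sigmoidoscopy, patients will be asked to record the previous 3 days" of food and drink. That record covers days I − 3 to I − 1, while the washout covers days d − 7 to d − 1. The overlap is 2 of 7 days if d = I − 1, 1 day if d = I − 2, and none if the drink is earlier. The same paragraph also asks for a daily intake record without stating its period. If that ran from Baseline, food and drink would be covered on up to 6 of the 7 washout days on the day-7 schedule. Neither record mentions medicines.

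**The case against.** The strongest reply is that the washout rule is mandatory and limits the free choice of day. Read together, the two texts mean that a subject who has not abstained for 7 days may not yet drink. The window allows Initiation on days 8 to 14, where compliant mornings exist. The study design overview supports this: "Patients fulfilling the inclusion and exclusion criteria will undergo" the assay, which can be read as placing it after screening. This stands in part. A reader might infer that the protocol makes compliance impossible or licenses an early drink; the document supports neither. But a drink that must follow a 7-day screening period and precede Initiation also rules out Initiation on day 7, so this reading does not rescue the nominal schedule. The Baseline bullet, which is the operative instruction, does not repeat the limit.

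A second reply is that washout may begin earlier. The recruitment phone script and any test instruction sheet are not in the document, and its silence does not prove that no instruction was given. That is fair, and subjects who already abstain comply at both tests. Nothing in the text starts the washout before Baseline, however.

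Third, lead time is opportunity, not abstinence. The document does not say when subjects are told to stop before either test, so the 21 to 27 days do not show that the post-diet test is clean. This also stands. The supplied-items-only rule supports some asymmetry for alcohol only.

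Finally, the consequence is unquantified. The best-case shortfall is 1 day, regular NSAID users are excluded, and LacMan sits beside tight-junction mRNA, immunofluorescence, serum LPS and zonulin, with none named as primary. A reader might infer that baseline LacMan is biased so as to favour the diet. The document gives neither a direction nor a size for any such effect.

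**Conclusion.** The point holds in limited form. With Initiation on its nominal day, abstention started at Baseline falls 1 to 6 days short of the plan's own 7-day rule, while the post-diet test has 21 to 27 days of lead time. Both requirements are met only if Initiation is on day 8 or later with a suitably late drink, or if the subject was already abstinent.

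This rests on two assumptions: abstention starts at Baseline, and the drink is taken on a day before the Initiation day. It supports saying that incomplete washout could fall more on the baseline LacMan value in an uncontrolled pre/post comparison, and that current records could only partly reveal it. It does not support a claim that LacMan is biased by any stated amount or in any stated direction, or that the other permeability measures are affected. The plan should be changed because its nominal schedule cannot meet its own rule for these subjects and the correction is small.

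**What to change.** 1. In the Baseline Visit bullet and any instruction sheet, allow the sugar drink no earlier than day 7 after Baseline, unless 7 prior abstinent days are documented.
2. For subjects not already abstinent, schedule Initiation on days 8 to 14. Day 8 suffices on calendar-day counting, because a day-7 morning drink completes its 24-hour collection on the morning of day 8. Day 9 or later is needed only if full 24-hour days are counted, with the drink then on day 8 or later.
3. At each test, record alcohol, aspirin and NSAID use in the preceding 7 days. This would also identify subjects on daily baby aspirin.

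The cost is a wording change and one short exposure question at each test, with no extra visit or sample. For subjects not already abstinent, the baseline period runs at least 1 day longer than nominal (8 − 7), or at least 2 days (9 − 7) under the stricter count. Both stay inside the existing +/- 7 day window but use up some of its scheduling tolerance.

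### Minor: the plan's only tests for proportions assume independent groups, so they would be wrong for any before-versus-after proportion

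*Combined protocol and SAP*

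**What the plan says.** The statistical analysis paragraph of Section 3.B sets out tests by type of variable.

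- Normally distributed continuous data "will be compared pre-and post-dietary interventions using paired Student's t-test".
- For the rest: "Continuous data which are not normally distributed will be presented as median (range) and compared using Wilcoxon signed-rank test".
- For categorical data: "Proportions will be expressed as percentages and compared using chi-square test or fisher exact test as appropriate".

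On sample size the paragraph states that "we based our power analysis on pre-post comparisons using paired t-tests".

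The design in Section 3.A is mainly within-patient: "Forty consenting IBS-D patients and twenty consenting IBS-C patients will undergo a 7-day screening period", and those who qualify are measured before and after a four-week diet. It also has comparisons between separate groups. The IBS-C Arm text says that "as a disease comparison group, 20 patients with IBS-C will be enrolled in the study". For the healthy controls, the microbiome subsection says "Their microbiome will be compared with microbiome of IBS-D patients pre and post LFD".

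No paired test for proportions, such as McNemar's, is named anywhere in the document.

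**The concern.** The first two rules are paired tests and the power calculation is paired. The rule for proportions names only tests for independent groups. The qualifier at its end most naturally means the choice between chi-square and Fisher, not a provision for paired data.

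If a proportion is compared before versus after in the same patients, both named tests treat 40 patients measured twice as 80 separate people. The p-value then depends only on the two totals and ignores how many patients changed in each direction, which is where the information about change lies. When a patient's two results are positively correlated, the test is too conservative and a real change can be missed. When they are negatively correlated, chi-square rejects too often.

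**Working it through.** **Inputs from the documents.** 40 IBS-D and 20 IBS-C patients (Section 3.A, before dropout); two-sided 5% level; the plan's power statement of n=20, d=0.5, r=0.7, 80% (Section 3.B).

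**Inputs assumed.** The document gives no rate or within-patient correlation for a binary outcome. I use a change from 70% to 50% for power, 60% at both times for type I error, and phi (the correlation between a patient's two binary results) of −0.2 to 0.45.

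**1. The plan's own figure.** The standardised within-patient effect is d/√(2(1−r)) = 0.5/√0.6 = 0.6455. With n=20, the noncentral t gives 78.2% power and the normal approximation 82.3%. The stated 80% is reproduced. It rests on the paired t-test, so the rule for proportions does not touch it.

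**2. One pair of totals, two different data sets.** Suppose 28/40 have a feature before the diet and 20/40 after.

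- Pearson chi-square: pooled rate 48/80 = 0.6; 0.2² / (0.6×0.4×2/40) = 0.04/0.012 = 3.33, p=0.068. Fisher p=0.110. Neither changes with the pairing.
- 10 lose and 2 gain the feature (phi 0.44): exact McNemar 2×(1+12+66)/4096 = 0.039. Mid-P subtracts the probability of the observed split, 66/4096 = 0.016, giving 0.022.
- 14 lose and 6 gain (phi 0): exact McNemar 0.115, mid-P 0.078.

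The difference is 20 percentage points in both. The independent-groups Wald 95% CI is −1 to 41 points in both: 0.2 ± 1.96×√(0.7×0.3/40 + 0.5×0.5/40). The paired (Bonett-Price) 95% CI is 3 to 36 points in the first case and −2 to 40 in the second.

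**3. Why the direction depends on phi.** The true variance of the difference is [p₁(1−p₁) + p₂(1−p₂) − 2·phi·√(p₁(1−p₁)p₂(1−p₂))]/n. Chi-square leaves out the last term. With equal rates, the true variance is (1−phi) times what chi-square assumes, so the real type I error is about P(|Z| > 1.96/√(1−phi)). That gives 7.4% at phi −0.2, 2.8% at 0.2 and 0.8% at 0.45.

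**4. Exact results.** These come from enumerating every paired 2×2 table, with uncorrected chi-square and Fisher applied to the two totals.

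Type I error, 60% at both times, n=40:

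| phi | Chi-square | Fisher | McNemar mid-P |
|---|---|---|---|
| −0.2 | 7.6% | 4.8% | 4.5% |
| 0 | 5.2% | 3.0% | 4.6% |
| 0.2 | 3.0% | 1.5% | 4.7% |
| 0.45 | 0.9% | 0.4% | 4.2% |

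Power, 70% to 50%:

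| n | phi | Chi-square | Fisher | McNemar mid-P | McNemar exact |
|---|---|---|---|---|---|
| 40 | 0 | 46% | 37% | 42% | 35% |
| 40 | 0.2 | 45% | 35% | 52% | 43% |
| 40 | 0.45 | 44% | 32% | 67% | 58% |
| 20 | 0 | 25% | 16% | 22% | 15% |
| 20 | 0.2 | 22% | 14% | 26% | 17% |
| 20 | 0.45 | 18% | 10% | 32% | 20% |

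For 70% to 50%, mid-P overtakes chi-square at phi of about 0.08 (n=40) and 0.10 (n=20). For 80% to 60% and 90% to 70%, the break-even is 0.04 to 0.10 at n=40 and 0.17 to 0.26 at n=20.

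**The case against.** The strongest reply is that no scheduled analysis is affected. The before-after outcomes in Section 3.A are the lactulose-mannitol ratio, gene expression, signal intensity, serum markers, cell frequencies, diversity metrics and symptom scores. All are continuous values or scores for each patient. The one outcome cut-off in the text, IBS-SSS of at least 175, is an entry criterion that every eligible patient meets at baseline. Diet compliance is yes/no but has no baseline counterpart. The proportions sentence does not itself mention before and after, and can be read as meant for comparisons between the three groups, where it is correct.

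This stands as far as severity goes: the defect is an omission with no named endpoint behind it. It does not remove the defect. The signed-rank sentence does not mention before and after either, yet it is plainly paired. The plan expects only most, not all, of its tests to be on continuous data. Daily stool form and the diarrhea items, collected at both times, are easily reported as proportions, and the only written rule for those would be the wrong one.

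A second reply is that the gain depends on assumed rates, an assumed phi and the choice of mid-P. That is fair. Exact McNemar has less power than uncorrected chi-square at phi 0.2 at both sample sizes, and gains only 2 points at n=20 and phi 0.45. It does beat Fisher at phi 0.2 and 0.45. The plan's r=0.7 concerns continuous outcomes and does not fix phi, though it suggests positive correlation is expected. A paired test is needed for validity; mid-P is the version that also recovers power at these sample sizes.

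**Conclusion.** The concern holds, as a minor point. For any within-patient proportion, the stated rule gives a p-value and interval that ignore the pairing. Under the assumed change from 70% to 50% with phi 0.45, chi-square falls 23 points of power below mid-P McNemar at n=40 (44% against 67%) and 14 points at n=20 (18% against 32%). At phi 0 mid-P is slightly weaker: 42% against 46%, and 22% against 25%. With positive correlation the consequence is missed changes; chi-square clearly exceeds 5% only if the correlation is negative (7.6% at phi −0.2). All these sizes rest on assumed rates and correlations and on full enrolment without dropout. The continuous analyses, the sample size and any comparison of proportions between independent groups are unaffected.

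**What to change.** In Section 3.B, replace the sentence on proportions with: 'Within-patient pre-post proportions are compared by McNemar's test (mid-P) with the paired difference and its 95% CI; chi-square or Fisher's exact test is used only between independent groups.'

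The cost is one sentence and a line of code, with no new data and no change to the sample size. The downside is the small loss of power relative to chi-square when within-patient correlation is near zero. Naming the test in advance also spares the analyst from having to depart from the written plan once the data are in.
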